2.2.2.2 Clinical Experience

Seven Phase I or II studies have evaluated selumetinib monotherapy both as a free base suspension (5 studies) or as Hyd-Sulfate capsule formulation (2 studies). Three Phase I or II studies have investigated the selumetinib Hyd-Sulfate capsule formulation in combination with a wide range of other cancer therapeutics. Refer to the selumetinib Investigators Brochure for detailed summaries. The MTD of selumetinib Hyd-Sulfate salt capsule was 75 mg bd. Selumetinib has not been given in combination with vandetanib before.

2.2.2.3 Clinical Pharmacokinetics

The pharmacokinetics of selumetinib were approximately dose proportional for both formulations. Selumetinib had a *t*_{max} of 1.5 hours, and *t*_{1/2} of 5 to 7 hours. Clearance (CL/F) and steady-state volume of distribution (V_{ss}/F) remained largely consistent across the dose range studied. *N*-desmethyl selumetinib PK profile was largely similar to selumetinib, but exposures were much lower. The plasma pharmacokinetic parameters for selumetinib and selumetinib *N*-desmethyl were similar after single and multiple dosing, suggesting minimal accumulation over time. A food effect study involving administration of selumetinib to patients with advanced solid malignancies under fasting conditions and with a high-fat meal indicated a statistically significant effect of food on the exposure of selumetinib. Geometric least squares mean (Glsmean), C_{max} and area under the plasma concentration-time curve (AUC) were reduced by 62% and 19%, respectively, under fed conditions. Therefore selumetinib should be taken with water on an empty stomach for 2 hours prior to dosing and 1 hour after dosing.

2.2.2.3.1 Exposure in subjects of Asian ethnicity

The pharmacokinetics of selumetinib were investigated in study D1532C00086, conducted in the UK involving healthy volunteers of Asian ethnicity (defined as being born in an Asian country, and expatriate for not longer than 5 years, and with maternal and paternal grandparents of Asian ethnicity). The subjects who received Selumetinib in Study D1532C00086 were of the following ethnicities: Japanese, Chinese, Filipino, Malay, Malaysian, Maldivian, Singaporean, Thai, Indian and Vietnamese, and it is not known in these groups whether Selumetinib exposure will be similar to Western subjects or to subjects of the specific Asian ethnicities included in Study D1532C00086.

The pharmacokinetic findings from study D1532C00086 do not support excluding subjects of Asian ethnicity from studies of Selumetinib. However, as it is possible that Asian subjects may experience higher Selumetinib plasma exposure (than would be expected in Western subjects receiving the same dose of selumetinib), there could be a potential for a higher risk of adverse events.

The number of Asian patients with advanced cancer who have received treatment with selumetinib is very low. Emerging information from ongoing study D1532C00067 of Japanese patients receiving selumetinib + docetaxel for second-line treatment of NSCLC suggests that febrile neutropenia may occur more commonly in Japanese patients (3 of 8 patients treated, although comparative data in Japanese patients receiving docetaxel

monotherapy is not available) than might be predicted from studies conducted in Western subjects.

Patients of Asian ethnicity are not excluded from studies evaluating selumetinib. However, when considering enrolling an individual of Asian ethnicity to a selumetinib clinical study, investigators should make a clinical judgment as to whether the potential risk of experiencing higher selumetinib plasma levels outweighs the potential benefit of treatment with selumetinib. The Patient Information and Consent form for studies of selumetinib includes information on the possibility of higher selumetinib plasma levels and occurrence of adverse events in Asian subjects than in subjects who are not of Asian origin. Investigators should be aware of the potentially higher risk of adverse events when monitoring patients of Asian ethnicity receiving treatment in clinical studies of selumetinib.

2.2.2.4 Safety

The maximum tolerated dose (MTD) of selumetinib was 100 mg bd as a free-base suspension and 75 mg bd as a Hyd-Sulfate salt capsule. Safety data have been evaluated from four Phase I studies and four Phase II monotherapy studies. The most frequently reported AEs in Phase II monotherapy studies with the free-base suspension formulation and Phase I monotherapy studies of both formulations were fatigue, dermatitis acneiform, nausea, diarrhoea, vomiting and peripheral oedema. Small mean increases in systolic and diastolic blood pressure have been observed in patients on selumetinib. No clinically significant trends were observed for pulse rate in any study. Review of ECG parameters demonstrated no evidence of QTc prolongation. A trend towards elevated liver transaminases has been observed in patients who received bd dosing of selumetinib. The majority of transaminase elevations reported either remained within normal limits or increased by no more than a single Common Terminology Criteria (Version 3) for Adverse Events (CTCAE) grade. There was a trend towards a small mean decrease in albumin and in some patients an increase in serum phosphate that was observed after initiation of selumetinib. Refer to the current version of the selumetinib IB for detailed summaries of AEs.

2.2.2.5 Efficacy

There were no significant differences in the primary endpoints of four Phase II monotherapy studies (see current version of the selumetinib IB) comparing selumetinib free-base suspension formulation with standard chemotherapy regimes in melanoma, pancreatic cancer, colorectal cancer, or NSCLC [D1532C00003, D1532C00008, D1532C00011 and D1532C00016].

However, objective responses were seen in both the melanoma and NSCLC studies. In the Phase II melanoma study (D1532C00003) (Dummer *et al* 2008) 6 partial responses were noted in patients treated with selumetinib (out of 104 patients enrolled), 5 of which were in patients with the *BRAF* mutation. In the Phase II NSCLC study (D1532C00016), 2 patients treated with selumetinib (out of 40 enrolled) had a partial response (mutation status unknown).

One patient in the Phase I Study D1532C00005 treated with selumetinib capsule formulation (75 mg bd) had a complete response (out of 31 patients enrolled). This patient had a BRAF+ melanoma. In another Phase I study with selumetinib capsule formulation assessing the effect of food on the dosing with selumetinib (D1532C00020), 2 patients with melanoma had a partial response (out of 28 patients enrolled).

2.3 Rationale for the proposed trial

2.3.1 Proposed Combination Hypothesis for Vandetanib and Selumetinib

The proposed combination hypothesis is that combined inhibition of VEGF, EGF and MEK signalling in an unselected NSCLC patient population (refractory to first-line therapy) may deliver greater benefit than inhibition of any of these targets alone.

The primary aim of the expansion cohort is to demonstrate the effective targeting of EGFR, VEGF and MEK signal transduction through pharmacodynamic end points. The study is not powered sufficiently to deliver definitive clinical efficacy data and thus it is not essential to enrol a homogenous patient population. However, it would be important to have imaging and biomarker evidence to test the rationale of multiple pathway inhibition. Inclusion of patients, for example, who have had previous EGFR targeted therapy (and would normally be resistant to EGFR Tyrosine Kinase Inhibitors (TKIs)) and those who are EGFR TKI naïve and properly informed would be helpful. Having a less restrictive inclusion criteria would also significantly enhance the recruitment rate.

Inhibition of EGFR signalling has been shown to benefit NSCLC patients with activating mutations in the EGFR tyrosine kinase domain or those with high EGFR gene copy number (Mok *et al.*; 2009). There is mounting evidence that NSCLC patients with mutant *KRAS* are less likely to respond to EGFR signalling inhibition (Roberts *et al.*; 2010). The correlation is even more clear-cut in metastatic colorectal cancer where patient tumours containing *KRAS* mutations clearly do not respond to treatment with the anti-EGFR monoclonal antibodies cetuximab or panitumumab. This resistance is presumed to be due to the activation of pathways downstream of RAS such as MEK/ERK being driven by the mutant *KRAS* rather than the EGFR. Conversely, preclinical data indicates that tumour cell lines and human tumour xenografts with *BRAF* or *KRAS* gene mutations tend to be sensitised to MEK inhibition, because of their constitutive activation and dependency on ERK pathway signalling. However, some tumour cell lines have been identified (head and neck squamous cell carcinoma and colorectal carcinoma cells) that lack *BRAF* or *KRAS* gene mutation yet retain sensitivity to MEK inhibition, and these also tend to be sensitive to EGFR tyrosine kinase inhibitors.

VEGF signalling is believed to be a pivotal angiogenic factor that can induce the growth, survival and permeability of tumour blood vessels, required to support the progression of solid tumour disease. The monoclonal antibody bevacizumab that specifically sequesters VEGF-A, has been shown to improve survival in NSCLC patients when combined with standard paclitaxel and carboplatin chemotherapy (Sandler *et al.*; 2006). Clinical data from patients with metastatic colorectal cancer suggest that the response to VEGF inhibition is not influenced by *KRAS* gene status.

[figure not shown]
Consequently, combined inhibition of VEGF signalling, EGFR signalling and MEK signalling may deliver benefit in NSCLC patients.

2.3.2 Combination Non-Clinical Anti-Tumour Activity

The addition of MEK inhibition to inhibition of either EGFR or VEGFR signalling was initially studied by examining selumetinib in combination with gefitinib (a selective EGFR tyrosine kinase inhibitor) or cediranib (a potent VEGFR tyrosine kinase inhibitor without activity against EGFR). A combination efficacy study of selumetinib and gefitinib was performed *in vivo* using an A549 human NSCLC model (*KRAS* mutant). The A549 tumour cell line is comparatively insensitive to monotherapy treatment with selumetinib or gefitinib alone, and when grown as a human tumour xenograft, demonstrates only modest sensitivity to treatment with either agent. However, a combination of selumetinib and gefitinib demonstrates a greater anti-tumour effect in this tumour xenograft model than either agent alone. A combination efficacy study of selumetinib and cediranib was performed in a Calu-6 human NSCLC model (*KRAS* mutant). This tumour line is sensitive to monotherapy treatment with selumetinib but not to treatment with an EGFR tyrosine kinase inhibitor (gefitinib), both *in vitro* and *in vivo*. Calu-6 tumour xenografts are also sensitive to treatment with a VEGFR tyrosine kinase inhibitor, such as cediranib, *in vivo*. When selumetinib and cediranib were dosed concomitantly in this model, the combination demonstrated a greater anti-tumour effect than either agent alone. Similar results have also been reported with this combination in orthotopic lung cancer models using NCI-H441 and NCI-H460 cells (both *KRAS* mutant) (Takahashi *et al*, 2011, Poster 629, AACR). However, in none of these studies was a direct statistical comparison of either monotherapy versus the combination performed and it is unclear if the combination efficacy was additive or synergistic relative to the two monotherapies.

Taken together the above three studies suggest that inhibition of MEK in combination with inhibition of either EGFR or VEGFR signalling and may give enhanced efficacy over either agent as a monotherapy. A similar or greater antitumour effect could therefore be expected for the combination of selumetinib with the dual EGFR and VEGFR inhibitor vandetanib. The efficacy of this combination was therefore examined in the A549 human NSCLC model (*KRAS* mutant). Although this tumour model is comparatively insensitive to selumetinib or gefitinib monotherapy, it does respond significantly to vandetanib – which can be attributed to inhibition of VEGF signalling. Dose groups were vehicle control selumetinib alone (25 mg/kg, PO once daily), vandetanib alone (25 mg/kg, PO once-daily), and a combination of selumetinib (25 mg/kg, PO once daily) plus vandetanib (25 mg/kg, PO once-daily). Growth inhibition was calculated from the start of treatment by comparison of the mean change in tumour volume for control and treated groups. The addition of selumetinib to vandetanib was found to induce a 35% increased anti-tumour effect versus vandetanib alone (Figure 1.) The tumour growth inhibition in the combination group was significantly greater ($p<0.005$; two-tailed t-test) than that in the vandetanib group.

Figure 1. Effect of administration of selumetinib (AZD6244; 25 mg/kg; orally once-daily), vandetanib (AZD6474; 25 mg/kg; orally once-daily), or a combination of the two, in on tumour size in A549 human NSCLC tumour xenografts.

***P<0.0005 relative to vehicle control. To remove any size-dependency prior to statistical evaluation, data was log-transformed prior to statistical evaluation using a one-tailed two-sample t test.; one-tailed t-test

When body weights were examined, treatment with selumetinib did not induce weight loss relative to the control group and weight loss in animals receiving a combination of selumetinib and vandetanib was comparable to the weight loss observed with vandetanib alone. Two out of ten animals in the combination group were sacrificed early due to bloated abdomens and subsequently found to have fluid within their peritoneal cavity at autopsy. Such an effect has been observed as a consequence of amyloidosis at a low level in untreated athymic mice and the two cases in the combination arm of this study may be an exacerbation of this condition. Further studies investigating the toxicology of vandetanib and selumetinib in combination have not been conducted due to the late stage patient population in the trial. This is in accordance with the Note for guidance on non-clinical evaluation for anti-cancer pharmaceuticals (EMEA/CHMP/ICH/646107/2008; 2008).

2.3.3 Clinical experience of Vandetanib and Selumetinib Combination

Vandetanib and selumetinib have not been given in combination to patients.

2.3.4 Possible toxicities based on single agent studies

AEs related to the skin, gastrointestinal system, cardiovascular systems and fatigue are commonly observed with both agents.

Clinical administration of both agents has been associated with skin toxicities with dermatitis acneiform and photosensitivity reaching CTCAE (version 3.0) Grade ≥ 3 in vandetanib and the former also being the most common AE in selumetinib trials. The co-administration of vandetanib and selumetinib may result in a higher frequency or intensity of these dermatological adverse events, especially dermatitis acneiform and rash. Similarly, administration of both agents has been associated with gastrointestinal adverse events and

the co-administration of vandetanib and selumetinib may result in a higher frequency or intensity of these gastrointestinal adverse events, especially nausea and vomiting.

Cardiovascular adverse events in Phase III trials of vandetanib include hypertension, deep venous thrombosis, pulmonary thrombosis, pulmonary haemorrhage, peripheral ischaemia and cerebrovascular events. Hypertension is considered to be a class effect for VEGF pathway inhibitors. Prolongation of the QTc interval, using Bazett's correction, was seen in Phase II studies. Two cases of torsade de pointes (both reversible and non-fatal) have been reported out of more than 4000 patients who have received vandetanib. No significant changes in heart rate were observed. Hypertension has also been observed in clinical studies of selumetinib. Some patients receiving selumetinib have been observed to develop asymptomatic decreases in left ventricular ejection fraction (LVEF) in the absence of obvious confounding comorbidities. Patients receiving selumetinib frequently report the development or worsening of oedema, particularly at peripheral sites or the face. The underlying aetiology of the oedema and fluid accumulation adverse events is unclear at present. There is currently no evidence to suggest that the oedema is due to congestive cardiac failure. The co administration of vandetanib and selumetinib may result in a higher frequency or intensity of these cardiovascular adverse events, especially hypertension.

In addition studies of vandetanib monotherapy occurrences of dyspnoea, pneumonia and interstitial lung disease were reported in some cases CTCAE (version 3.0) Grade ≥ 3 . There is also data from a pharmacoethnicity study suggesting that interstitial lung disease may occur more often in patients from Japan than in patients from elsewhere. Dyspnoea and interstitial lung disease have been reported in patients receiving selumetinib, although the majority of these events have occurred in patients with lung/pleural disease due to their underlying malignancy. The combination of two agents with this finding may result in a higher frequency or intensity of these adverse events.

The gastrointestinal AE's observed with both agents does raise the possibility of an interaction of the combination on the absorption one or both agents. Additionally both vandetanib and selumetinib have been shown to induce CYP3A4 and selumetinib is a substrate of CYP3A4 raising the possibility of metabolic interaction. Pharmacokinetics of both agents and the two most abundant metabolites of each will be performed during the study to detect any such interactions.

2.3.5 Supportive combination class data

Preliminary clinical data are available for a combination study of selumetinib with the EGFR inhibitor erlotinib. A total of 48 patients received treatment with selumetinib in combination with erlotinib 100 mg once daily (Study D1532C00004). Doses of 50 mg bd and 75 mg bd selumetinib were explored in combination with erlotinib however the combination of selumetinib 50 mg bd and erlotinib to be non-tolerated (due to Grade 3 rash and diarrhoea). The tolerability of once daily dosing of selumetinib 50, 100 or 150 mg was subsequently explored in combination with erlotinib. All patients who received chronic administration of selumetinib 150 mg bd and erlotinib experienced either Grade 2 or 3 adverse events of rash and/or diarrhoea and/or mucositis, which required dose interruptions and reductions in some patients; therefore, this dose combination was not recommended for use in clinical trials.

The most common AE across all selumetinib doses were diarrhoea and rash. There was no evidence of a PK interaction between selumetinib and erlotinib.

A preliminary review of the available safety data indicated that the adverse event profile for the combination of selumetinib with erlotinib is consistent with the individual monotherapy profiles for these agents. Selumetinib 100 mg once daily is the recommended dose for combination with erlotinib 100 mg once daily.

2.3.6 Marketing Experience

Selumetinib had not received marketing approval in any country or region (at the time of development of this protocol). In 2015, the FDA granted Orphan Drug Designation for selumetinib, for the treatment of uveal melanoma.

Regulatory submissions for vandetanib in combination with chemotherapy in patients with advanced NSCLC were submitted to the FDA and the EMA in June 2009 and withdrawn in October 2009.

The FDA and the EMA accepted regulatory submissions for review of vandetanib in the treatment of patients with advanced medullary thyroid cancer (MTC) in September 2010. Vandetanib has recently received FDA marketing approval (100 mg and 300 mg tablets) for treatment of symptomatic or progressive medullary thyroid cancer in patients with unresectable locally advanced or metastatic disease.

3 TRIAL DESIGN

This is a Phase I, multi-centre, dose escalation study (any solid tumour) with an expansion cohort (NSCLC). The expansion cohort will include functional imaging and assess tumour and blood biomarkers of both vandetanib and selumetinib.

3.1 Clinical trial objectives and endpoints

Primary objectives and endpoints

Primary objectives	Endpoints
Assessing the safety and toxicity profile of the combination of vandetanib and selumetinib.	Determining causality of each adverse event to vandetanib or selumetinib and grading severity according to NCI CTCAE Version 4.02
To propose a recommended dose and schedule for Phase II evaluation of the combination of vandetanib and selumetinib.	Determining the MTD of the combination of vandetanib and selumetinib as proposed by the protocol. OR the single agent recommended Phase II dose (RP2D) of vandetanib in combination with the single agent RP2D of selumetinib.

Secondary objectives and endpoints

Secondary objectives	Endpoint
Determine the plasma PK profiles of vandetanib and selumetinib and their metabolites	PK parameters during Cycle 1 including Cmax and AUC pre and post treatment with vandetanib alone and following the combination of vandetanib and selumetinib. Parameters to be measured include: 
• vandetanib• selumetinib and N-desmethyl metabolite. (other metabolites may be measured as determined during the study).
Expansion cohort To evaluate progression free survival (PFS) of patients with NSCLC after treatment with the combination of vandetanib and selumetinib.	Determine PFS at 12 weeks (from date of first dose of vandetanib) by RECIST (Response Evaluation Criteria In Solid Tumors) criteria.
Expansion cohort To evaluate the survival rate of patients with NSCLC after treatment with the combination of vandetanib and selumetinib.	Determine the one year survival rate.
Expansion cohort To assess the tumour metabolism in patients with NSCLC.	Measurement of tumour metabolism using CT FDG-PET imaging during Cycle 1 pre and post treatment with vandetanib alone and following the combination of vandetanib and selumetinib.

Tertiary objectives and endpoints

Tertiary objectives	Endpoint
[REDACTED]	[REDACTED]

3.1.1 Definition of dose limiting toxicity

The dose limiting toxicity (DLT) and maximum tolerated dose (MTD) are defined using the National Cancer Institute (NCI) Common Terminology Criteria for Adverse Events (CTCAE) Version 4.02.

During the dose escalation phase, DLTs identified in Cycle 1 of combination treatment will inform the decisions to dose escalate through the increasing dose levels. DLTs will be defined throughout the treatment period during dose escalation and in the expansion cohort and will be considered in determining the RP2D. The criteria by which DLTs will be assessed against during Cycle 1 for dose escalation decisions are as follows:

A DLT is defined as an adverse event considered highly probable or probably related to vandetanib or selumetinib, that occurs during the first cycle of combination period:

- Death
- Neutropenia Grade 4 for ≥ 5 days duration (absolute neutrophil count (ANC) $<0.5 \times 10^9/L$) *

- Febrile neutropenia (fever of unknown origin without clinically or microbiologically documented infection) with Grade 3 or 4 neutropenia (absolute neutrophil count [ANC] $<1.0 \times 10^9/L$ and fever $\geq 38.5^{\circ}\text{C}$);
- Infection (documented clinically or microbiologically) with Grade 3 or 4 neutropenia (ANC $<1.0 \times 10^9/L$)
- Thrombocytopenia Grade 4: a) for ≥ 5 days *See footnote, or b) associated with active bleeding, or c) requiring platelet transfusion.
- Grade 3 or 4 toxicity to organs other than the bone marrow including Grade 3 and Grade 4 biochemical AEs.
- Grade 4 diarrhoea
- Any drug related toxicity that causes a treatment interruption for > 2 weeks (14 successive days). If a patient is deemed fit to restart treatment on Day 15 then this is not a DLT.
- QTc prolongation >500 msec
- Grade 4 hypertension.
- Persistent hypertension (defined as blood pressure $>160/100$ mmHg) sustained for >1 week despite optimal therapy.

EXCLUDING:

- Grade 3 nausea
- Grade 3 or 4 vomiting in patients (who have not received optimal treatment with anti-emetics)
- Grade 3 skin toxicity (and patients are receiving supportive measures to manage toxicity)
- Grade 3 diarrhoea in patients (who have not received optimal treatment with anti diarrhoeals)
- Alopecia (any grade)

*** Note: In the event of a Grade 4 neutropenia or Grade 4 thrombocytopenia, a full blood count must be performed within 5 days of the onset of the event to determine if a DLT has occurred. Continue to monitor the patient closely until resolution to Grade 3 or less.**

Should any change be made to the grade or causality of an AE during the trial that may alter its DLT status, the Centre for Drug Development (CDD) must be informed immediately as this may affect dose escalation decisions.

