1.4.3 Treatment period – Cycle length

Cycle 1 will consist of 42 days. This includes the 14 days of vandetanib alone plus the 28 days of combination treatment.

Subsequent cycles will be of 28 days in length and consist of continuous combination treatment with vandetanib and selumetinib at steady state from Day 1. There is no planned interval between cycles. Patients may continue to receive the combination therapy in the absence of disease progression or unacceptable toxicity.

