7.2.1.1 Evaluations during Day 1 (Prior to first dose of vandetanib)

Required for dose escalation and expansion cohorts

- Physical examination: symptom-directed physical examination.
- WHO performance status, temperature, pulse rate, BP (sitting).
- Haematology tests: detailed in Section 7.1.4;
- Biochemistry tests: detailed in Section 7.1.4;

Expansion cohort (Cycle 1) ONLY

- [REDACTED]

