7.2.1.3 Evaluations during Day 12 (+/- 2 days)

Expansion cohort (Cycle 1) ONLY

- [REDACTED]
- [REDACTED]
- [REDACTED]
- [REDACTED]

7.2.1.4 Evaluations on Day 15 (prior to first dose of vandetanib and selumetinib in combination)

Required for dose escalation and expansion cohorts

- Physical examination: symptom-directed physical examination.
- WHO performance status, temperature, pulse rate and BP (sitting).
- ECG
- Haematology tests: detailed in Section 7.1.4;
- Biochemistry tests: detailed in Section 7.1.4;
- Urinalysis –glucose, protein and blood

Dose escalation cohort (Cycle 1) ONLY

- **Pharmacokinetics (blood sampling):** (see Section 8.3 for specific time points)

7.2.1.5 Evaluations on Day 22

Required for dose escalation and expansion cohorts (Cycle 1 and 2 only)

- Haematology tests: detailed in Section 7.1.4;
- Biochemistry tests: detailed in Section 7.1.4;
- Ophthalmological exam: detailed in Section 7.1.2 (+/- 2 days)

7.2.1.6 **Evaluations at Day 29**

Required for dose escalation and expansion cohorts (Cycle 1 and 2 only)

- Haematology tests: detailed in Section 7.1.4;
- Biochemistry tests: detailed in Section 7.1.4;
- ECG

Dose escalation cohort (Cycle 1) ONLY

- **Pharmacokinetics (blood sampling):** (see Section 8.3 for specific time points)

7.2.1.7 **Evaluations on Day 36**

Required for dose escalation and expansion cohorts (Cycle 1 and 2 only)

- Haematology tests: detailed in Section 7.1.4;
- Biochemistry tests: detailed in Section 7.1.4;

7.2.1.8 **Evaluations on Day 42 (+/- 5 days)**

Expansion cohort (Cycle 1) ONLY

- **Pharmacodynamics (optional tumour biopsies)** (See Section 8.4.1 for specific time points).
 - Three endobronchial samples from tumour tissue will be collected.

7.2.2 **Evaluations during Cycle 2**

Combination of vandetanib and selumetinib from Cycle 2 Day 1

Required for dose escalation and expansion cohorts

On the first day of Cycle 2, prior to dosing

- ECGs to be performed as clinically indicated but not less than pre C2 D1 of combination and pre Day 1 of every cycle.
- ECHO/MUGA scan (within 7 days prior to Cycle 2 Day 1 is acceptable)
- Ophthalmological exam (as per 7.1.2) (within 7 days prior to Cycle 2 Day 1 is acceptable).
- Physical examination: symptom-directed physical examination.
- WHO performance status, temperature, pulse rate and BP (sitting) and weight.

- **Weekly** laboratory tests
 - Haematology tests: detailed in Section 7.1.4;
 - Biochemistry tests: detailed in Section 7.1.4;

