7.6 Schedule of events (2)

Cycle 2 of combination (vandetanib and selumetinib) onwards

Observation/Investigation	Standard Evaluations for each cycle 1 cycle = 28 days (vandetanib and selumetinib treatment)				10 weeks* (Post end Cycle 2)	12 weeks	Off study and Follow-up	
	Day 1	Day 8	Day 15	Day 22			Off study: 28 days after last dose of IMP	Follow-up: monthly(s)
Adverse event evaluation	Continually review						X	Until resolution
Concomitant treatments	Continually review						X	
Radiological (CT, MRI, X-ray) disease assessment (to include thoracic CT) (m)	To be performed every two cycles				X		X (unless performed within previous 4 wks)	
Ophthalmological exam (n)	C2D1, C3D1 and as clinically indicated throughout study treatment for patients experiencing visual disturbances							
Clinical disease assessment (if applicable)	As clinically indicated						As clinically indicated	
Physical examination	On the first day of each cycle: symptom-directed physical examination						Symptom-directed physical examination	
Temperature, blood pressure and pulse	On the first day of each cycle						X	
Weight	On the first day of each cycle						X	
WHO performance status	On the first day of each cycle						X	
Laboratory tests: haematology and biochemistry (o)	X	X	X	X			X	To resolution of drug-related lab AEs
GFR assessment	As clinically indicated (calculated C&G/Wright and if applicable Isotope clearance measurement)							
Urinalysis	As clinically indicated						X	
Electrocardiogram (ECG) (p)	Prior to Day 1 of every cycle						X	
ECHO/MUGA (q)	C2D1 and then every 12 weeks (or more often as clinically indicated)							
Vandetanib administration (t)	Continuous daily dosing – Doses and schedule of each IMP to be confirmed by the Sponsor							
Selumetinib administration (t)	Continuous daily dosing – Doses and schedule of each IMP to be confirmed by the Sponsor							
Expansion cohort only (NSCLC patients)								

(m) Bone scan to be performed as clinically indicated.

(n) To include slit lamp assessment, visual acuity, visual fields, colour vision, optical coherence tomography and intraocular pressure. Examinations must be performed prior to Cycle 2 Day 1 and Cycle 3 Day 1 (within 7 days prior to C2D1 and C3D1 is acceptable). Additional eye examinations can then be performed as clinically indicated.

(o) Haematology and biochemistry to be assessed weekly during Cycle 1 and 2 and then prior to Day 1(-3 days time window) of subsequent cycles.

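### No blood pressure reading is scheduled between the pre-dose Day 15 check and Cycle 2 Day 1, so scheduled visits cannot show the sustained-hypertension DLT arising on the combination

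*Protocol*

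**What the plan says.** **The criterion.** Protocol Section 3.1.1 lists, among the DLTs, "Persistent hypertension (defined as blood pressure" above 160/100 mmHg) "sustained for >1 week despite optimal therapy". For escalation decisions, a DLT is an event "that occurs during the first cycle of combination period". Section 1.4.3 sets Cycle 1 at 42 days: "This includes the 14 days of vandetanib alone plus the 28 days of combination treatment". The window is therefore Days 15 to 42. Grade 4 hypertension is a separate DLT and is not the subject here.

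**The schedule.** Section 7.2.1.1 (Day 1) lists "WHO performance status, temperature, pulse rate, BP (sitting"), and Section 7.2.1.2 (Day 5) repeats it. The next reading belongs to "Evaluations on Day 15 (prior to first dose of vandetanib and selumetinib in combination"). The Day 22, 29 and 36 entries contain no blood pressure. Section 7.2.2 brings it back on Cycle 2 Day 1, before dosing, and from then on the Section 7.6 table has it "On the first day of each cycle".

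**The expectation.** Section 2.3.4 states: "The co administration of vandetanib and selumetinib may result in a higher frequency or intensity of these cardiovascular adverse events, especially hypertension".

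**The concern.** A criterion defined by duration under treatment needs repeat measurements: a raised value, treatment, and a further raised value more than a week later. The schedule supplies none of these while the patient is on the combination in Cycle 1. The protocol handles its other duration-based criteria differently. For Grade 4 neutropenia and thrombocytopenia, a note in Section 3.1.1 mandates a further blood count so that DLT status can be settled. Blood pressure has no counterpart.

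At stake is the completeness of the DLT count. Under Sections 3.1.2 and 3.2.1, two DLTs in up to six patients stop escalation and fix the MTD, which is a primary endpoint. If the hypertension criterion is picked up only where a site happens to measure blood pressure, the count depends on local habit in a multi-centre trial, for a toxicity that the protocol itself anticipates.

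**Working it through.** There is no design figure to reproduce. The check sets the visit lists against the DLT window.

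**1. Window.** 14 days of vandetanib alone + 28 days of combination = 42 days. The DLT window is Days 15 to 42, and Cycle 2 Day 1 is Day 43.

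**2. Blood pressure by visit (Sections 7.2.1.1 to 7.2.2, dose escalation).**

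| Day | Listed | Blood pressure |
|---|---|---|
| 1 | Examination, vital signs, bloods | Yes, before vandetanib |
| 5 (±1) | Examination, vital signs, ECG, bloods | Yes, vandetanib alone |
| 15 | Examination, vital signs, ECG, bloods, urinalysis, PK | Yes, before the first combination dose |
| 22 | Bloods, eye examination | No |
| 29 | Bloods, ECG, PK | No |
| 36 | Bloods | No |
| 42 (±5) | Expansion cohort only, optional biopsies | No |
| 43 (Cycle 2 Day 1) | Examination, vital signs, ECG, bloods, ECHO/MUGA, eye examination | Yes, before dosing |

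The Section 7.5 table is damaged in the available text. As far as it can be read, its blood pressure row has no mark after the one that lines up with Day 15. The visit-by-visit text settles the point. The redacted items in Section 7.2.1 sit in expansion-only blocks and so cannot hide a dose-escalation reading.

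**3. Count.** Scheduled on-combination readings in Days 15 to 42: 0. Gap between consecutive scheduled readings: 43 − 15 = 28 days, the length of the window. Readings needed to show persistence: at least two, more than 7 days apart. For both to fall inside the window, the first must be no later than Day 34 (42 − 34 = 8).

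**4. Would adding the three existing visits be enough?**
- Days 22 and 29: 7 days apart, which is not more than a week.
- Days 29 and 36: 7 days, likewise.
- Days 22 and 36: 14 days, qualifies.
- Days 29 and 43: 14 days, qualifies, but the second reading is outside the window.
- Days 36 and 43: 7 days, does not qualify.

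Adding the visits is necessary but captures only onset by Day 22 wholly inside the window. Later onset needs a timed repeat and a rule on the use of Day 43.

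**5. Possible effect on escalation (illustration).** The documents give no rate for this DLT, so all rates here are assumptions. Let *a* = 0.10 be the rate of other DLTs, *b* the rate of the blood pressure DLT and *d* the share of those detected, with the two types independent. The rate seen is p = 1 − (1 − a)(1 − b·d). Approximating the rule as passing on 0/3 or 1/6, with q = 1 − p:

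P(escalate) = q³ + 3pq² × q³

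| b | Detected | p | P(escalate) |
|---|---|---|---|
| any | none | 0.10 | 0.729 + 0.177 = 0.91 |
| 5% | all | 1 − 0.9 × 0.95 = 0.145 | 0.625 + 0.199 = 0.82 |
| 20% | half | 1 − 0.9 × 0.9 = 0.19 | 0.531 + 0.199 = 0.73 |
| 20% | all | 1 − 0.9 × 0.8 = 0.28 | 0.373 + 0.163 = 0.54 |

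The protocol uses a rolling-six design with three to six patients per level, so these values are approximate.

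**The case against.** The strongest reply is that the protocol has other ways to find raised blood pressure and to act on it.

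- Days 5 and 15 are read after vandetanib has started, and Section 2.3.4 calls hypertension a class effect of VEGF pathway inhibitors. A high value then can prompt treatment and follow-up that run into the window.
- Adverse events are reviewed at each visit (Section 7.2), and hypertension is handled under local policy (guidelines for other toxicities, under Section 5.4.1.1).
- Cycle 2 Day 1 blood pressure is taken before dosing. Section 5.4.1 requires eligibility parameters to be met before each cycle, and the exclusion criteria cover uncontrolled hypertension.
- Escalation reviews use all adverse events and other available data (Section 5.3), and later DLTs are considered for the recommended Phase II dose (Section 3.1.1).

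Much of this stands. A reader might infer that such hypertension must go unseen and that the cohort will then escalate. The documents do not support that: unscheduled readings are possible, and a high Day 43 value could reach the review.

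The gap remains all the same. Adverse event review and local policy do not require a measurement. Section 7 foresees weekly blood samples being taken at another hospital, so an incidental reading on Day 22 or 36 cannot be assumed. A single high value on Day 43 shows neither duration nor failure of treatment within Cycle 1. Days 5 and 15 cannot show onset after selumetinib starts.

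**Conclusion.** The point holds for scheduled assessments. A patient followed exactly to schedule has 0 on-combination blood pressure readings in the 28-day window, so hypertension that begins on the combination and lasts more than a week within Days 15 to 42 cannot be shown from scheduled visits. This DLT may be under-ascertained, to a degree that will vary by site. That conclusion rests only on the visit lists and the day arithmetic.

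The effect on escalation cannot be fixed from the documents. With 10% other DLTs assumed, complete non-detection raises the chance of escalating from 0.82 to 0.91 at a 5% rate of this DLT, and from 0.54 to 0.91 at 20%. If half are found at 20%, the figure is 0.73. It would be tempting to read 0.91 against 0.54 as the expected error. That is the extreme contrast, with an assumed high rate and every event missed.

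Severity: should be fixed. The criterion feeds a primary endpoint and the remedy is cheap, but one criterion is affected and partial safeguards exist.

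**What to change.** Reconcile Section 3.1.1 with the schedule:

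1. Add sitting blood pressure and pulse to the existing Day 22, 29 and 36 visits in Sections 7.2.1.5 to 7.2.1.7 and in the Section 7.5 table. Where bloods are taken at another hospital, have the reading taken there and returned with the results.
2. State that any value above the protocol's own threshold in the window is followed by a reading more than 7 days later. A repeat within a week cannot meet the definition.
3. State that the Cycle 2 Day 1 reading may be used to adjudicate an event that began in the window. A first high value on Day 36 still needs the later reading under item 2, because Day 43 is exactly 7 days on.

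This changes measurement and adjudication only; no threshold, dose or treatment rule is altered. The cost is a few minutes at three visits already planned, a few extra eCRF fields and an occasional repeat reading. Slightly more hypertension adverse events will probably be recorded, and an adjudication that uses Day 43 may hold a cohort decision briefly.
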